The study period consists of 6 weeks of screening, 52 weeks of treatment, and 2 weeks of follow-up, a total of 60 weeks. The treatment period consists of Treatment Period I (double-blind) from Week 0 to Week 12 and Treatment Period II (open-label) between Week 12 and Week 52. Subjects will visit the site at the start of the screening period (Week -6), Week -2 of the screening period, end of the screening period (Week 0), Week 2 and Week 4 of the treatment period, and at every 4 weeks until Week 52 of the treatment period, and at the end of the follow-up period (Week 54) (total of 18 visits).					
The planned sample size is 106 randomized subjects (53 per group).					
Objectives: To evaluate the efficacy and safety of SYR-472 when administered at a dose of 25 mg once weekly using placebo as a control in patients with type 2 diabetes mellitus complicated by severe renal impairment or end-stage renal failure and inadequate glycemic control despite diet and/or exercise therapy (if any) or despite treatment with 1 antidiabetic drug in addition to diet and/or exercise therapy (if any); and to evaluate the long-term safety and efficacy of SYR-472 when administered at a dose of 25 mg once weekly in patients with type 2 diabetes mellitus complicated by severe renal impairment or end-stage renal failure.					

Subject Population:

Patients with type 2 diabetes mellitus complicated by severe renal impairment or end-stage renal failure and inadequate glycemic control despite diet and/or exercise therapy (if any) or despite treatment with 1 antidiabetic drug in addition to diet and/or exercise therapy (if any)

Number of Subjects:	Number of Sites:
Randomized: 53 subjects per group, 106 in total (Changed as of 12 September 2016)	Approximately 50 sites
Dose Level:	Route of Administration:
<Treatment Period I> One SYR-472 25 mg tablet or placebo tablet will be orally administered once weekly before breakfast.	Oral
<Treatment Period II> One SYR-472 25 mg tablet will be orally administered once weekly before breakfast.	
Duration of Treatment:	Period of Evaluation:
<Treatment Period I> SYR-472 25 mg tablet or placebo tablet: 12 weeks	Screening period : 6 weeks Treatment Period I : 12 weeks Treatment Period II: 40 weeks Follow-up period : 2 weeks Total : 60 weeks
<Treatment Period II> SYR-472 25 mg tablet: 40 weeks	
Criteria for Inclusion:	
1. The subject has a diagnosis of type 2 diabetes mellitus.	

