In Study 101, the elimination half-life (mean) of unchanged SYR-472 following the administration of SYR-472 50 mg under fasted conditions (without breakfast) to patients with severe renal impairment and end-stage renal failure was 88.45 and 107.97 hours, respectively, which were longer than those in matched healthy adults (56.43 and 56.75 hours). Based on these results, the time of assessment at the end of the follow-up period was set at Week 54 by reference to 5 times the elimination half-life (18.4 and 22.5 days, or longer) from the last administration of SYR-472 25 mg tablets (Week 51).

(4) Justification for the primary endpoints

According to “the Guideline for Clinical Evaluation of Hypoglycemic Agents (Revised Draft)” [4], HbA1c should be used as an efficacy endpoint in phase 3 studies in principle. In addition, the safety of the study drug should be used as the primary endpoint in long-term studies. Therefore, HbA1c at the end of Treatment Period I will be evaluated as the efficacy endpoint and AEs throughout the treatment period will be evaluated as the safety endpoint.

(5) Justification for the secondary endpoints

In reference to “the Guideline for Clinical Evaluation of Hypoglycemic Agents (Revised Draft)” [4] and based on the results of clinical studies of SYR-472 conducted so far, HbA1c, fasting blood glucose, and glycoalbumin were set as efficacy endpoints, and vital signs, 12-lead ECG, and clinical laboratory test values were set as safety endpoints to evaluate the efficacy and safety of SYR-472 25 mg.

(6) Justification for the inclusion criteria

See Section 7.1.

(7) Justification for the exclusion criteria

See Section 7.2.

(8) Justification for the excluded medications and other exclusions

See Section 7.3.

(9) Justification for the sample size

See Section 13.3.

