- For subjects who are not using any other antidiabetic drug in Treatment Period I (those who are only treated with the study drug), the use of 1 new oral hypoglycemic drug* is allowed at Week 16 of the treatment period and thereafter.

*: Any 1 of the following medications: metformin, repaglinide, acarbose, miglitol, or voglibose

(2) Insulin Preparations

For subjects who are receiving insulin preparations at the start of the screening period (Week -6) and continue to receive in the study period, insulin preparations should be administered as specified below.

• Type of Insulin Preparation

Any 1 of the mixed (rapid-acting or ultrarapid insulin containing no more than 30% of volume), intermediate-acting, or long-acting soluble insulin preparations should be used alone, and should not be changed throughout the study period.

• Daily Dose (Unit) of Insulin Preparation

1) Screening Period

The daily dose (unit) of insulin preparation should be 40 units/day or less at the start of the screening period (Week -6), and the dose and regimen should not be changed during the screening period (for subjects on hemodialysis who receive different daily doses [unit] of insulin preparation on days of hemodialysis and on other days, each dose and regimen of insulin preparation should not be changed).

2) Treatment Period I

The dose and regimen of insulin preparations at the start of the screening period (Week -6) should be maintained and no changes will be allowed, in principle.

However, the investigator or sub-investigator should consider reduction or increase in the daily dose (unit) of insulin preparation if the criteria described below are met. After dose reduction or increase, the unit after reduction or increase should be continued.

Even if reduction in the daily dose (unit) of insulin preparation results in the discontinuation of insulin use, the study may be continued. If increase in the daily dose (unit) of insulin preparation results in a dose exceeding 40 units/day on a continuing basis, the investigator or sub-investigator should determine whether the study should be continued or discontinued, with respect to the safety of the subject.

Criteria for dose reduction: If either criterion (i) or (ii) described below is met, the daily dose (unit) of insulin preparation may be reduced from the unit administered at the start of the screening period (Week -6) by up to 4 units (regardless of the number of changes).

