9.3.6 Post Study Care

The study drug will not be available upon completion of the subject's participation in the study.

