1.2.4 Concomitant Antidiabetic Drugs Permitted in the Study

Analysis set: Full analysis set

Analysis variables: Newly added oral hypoglycemic drug [Yes, No]
in Treatment Period II (at Week 16
and thereafter)
Any change in antidiabetic drugs that [Yes, No]
are being used at Week -6 and will be
concomitantly used during the study
period in Treatment Period II

Stratum: Types of antidiabetic drugs [Rapid-acting insulin
secretagogues,
 α -glucosidase inhibitors,
Insulin preparations]

Analysis methodology: The following analysis will be performed for the newly added oral hypoglycemic drug in Treatment Period II (at Week 16 and thereafter) in subjects who are not using any antidiabetic drug at Week -16 among the full analysis set by treatment group. Also, the following analysis will be performed for any change in antidiabetic drugs that are being used at Week -6 and will be concomitantly used during the study period in Treatment Period II in subjects who are using antidiabetic drugs at Week -16 among the full analysis set by treatment group. Treatment Period II is the period from the start of the study drug administration for Treatment Period II until 20 days after the last administration of the study drug for Treatment Period II.

(1) Frequency distribution

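### The only table of Period II antidiabetic-drug changes includes subjects never dosed in Period II and does not separate increases from reductions

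*SAP*

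**What the plan says.** SAP 1.2.4 has two Yes/No rows, by treatment group, stratified by type of antidiabetic drug.

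- **New oral drug from Week 16 on.** Tabulated "in subjects who are not using any antidiabetic drug at Week -16 among the full analysis set by treatment group".
- **Change in a drug already in use.** Tabulated "in subjects who are using antidiabetic drugs at Week -16 among the full analysis set by treatment group". The variable is binary ("Any change in antidiabetic drugs that [Yes, No"; the cell is broken by the page layout).

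Period II is defined there as starting with the first Period II dose and running "until 20 days after the last administration of the study drug for Treatment Period II". Protocol 13.1.1 defines the full analysis set as subjects randomized and dosed at least once; Period II entry is not required.

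Protocol 7.3 allows background therapy to move either way in Period II. Insulin may be increased or reduced. Existing oral drugs may be changed in dose, interrupted or stopped. For subjects on no other antidiabetic drug in Period I, "the use of 1 new oral hypoglycemic drug* is allowed at Week 16 of the treatment period and thereafter".

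No other SAP output covers this. SAP 1.2.3 tabulates concomitant medications, which Protocol 9.1.7 defines as drugs other than study drug and antidiabetic drugs. SAP 1.3.2 tabulates compliance only.

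**The concern.** Long-term efficacy is a stated objective (Protocol 5.1). Period II is open-label with no control arm. SAP 2.2.1 reports HbA1c at each Period II visit, and the proportions below 6.0%, 7.0% and 8.0% at its end, without stratifying or censoring for added therapy. The HbA1c subgroups in SAP 2.4.8 concern Period I only. A reader asking how far a sustained HbA1c reflects study drug rather than other drugs therefore has only table 1.2.4.

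Two features limit that table. Its denominator includes people who could not have the event, which makes use of other drugs look less frequent than it was among those treated. And a Yes for change could mean more insulin, less insulin or a stopped oral drug, which have opposite implications for the HbA1c result.

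**Working it through.** **1. The 20-day cut-off against the HbA1c windows.**

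- Last scheduled dose at Week 51 (Protocol 6.2): Study Day 7 × 51 + 1 = 358.
- Week 52 visit: Study Day 365, and 365 - 358 = Follow-up Day 7.
- End of the table's Period II: 358 + 20 = Study Day 378.
- SAP window for Week 52 HbA1c: Study Days 351 to 378, up to Follow-up Day 20. The end-of-Period-II HbA1c also accepts data up to Follow-up Day 20.
- Follow-up visit on the 21st day after the last dose (Protocol 9.3.5): 358 + 21 = Day 379.

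The table's period therefore ends on the same day as the HbA1c window. For a completer sampled exactly on Day 365, 378 - 365 = 13 later days are also counted, which is a minor over-count.

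**2. Denominator.** Let p be the true proportion with an event among subjects dosed in Period II, and d the share of the tabulated population not dosed in Period II. If the latter all count as No, the table shows p × (1 - d).

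The documents give no d, so a range is assumed. The first value, 2/53 = 3.8%, is Protocol 13.3's allowance for subjects not evaluable for the primary endpoint (53 randomized, 51 evaluable per group). It is only a proxy.

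| d (assumed) | true 20% reads | true 50% reads |
|---|---|---|
| 3.8% | 19.2% | 48.1% |
| 5% | 19.0% | 47.5% |
| 10% | 18.0% | 45.0% |
| 20% | 16.0% | 40.0% |

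For the new-drug row, d also includes subjects who entered Period II but left before Week 16.

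The SAP handles the same issue differently elsewhere. In 3.1.1 and 3.3.2.3, analyses of events after the start of the SYR-472 25 mg tablet are limited to subjects who received it. The flag needed here already exists, because SAP 1.1.5.1 tabulates treated and not treated for Period II.

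**3. Direction.** No arithmetic applies. Protocol 7.3 permits increases, reductions, interruptions and stops; SAP 1.2.4 gives them one Yes. Stratifying by drug type does not recover direction.

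**4. Week -16.** Both populations are selected at Week -16, as is the one in SAP 1.3.2. Screening starts at Week -6, and the row label in 1.2.4 itself refers to Week -6. The two time points can classify a subject differently. Protocol 7.1 criterion 7 requires drug-free subjects to be so from 6 weeks before Week -6, that is, from Week -12. Someone who stopped a drug between Week -16 and Week -12 is a user at Week -16 but drug-free at Week -6, and would fall in the wrong row.

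**The case against.** **A stronger reading is tempting and does not hold.** A reader might infer that the 20-day extension inflates the table with drugs started after treatment ended, since the protocol places "Treatment Period II (open-label) between Week 12 and Week 52" and says "The study drug will not be available upon completion". The documents do not support this. The extension coincides with the outer limit of the HbA1c windows, and a shorter fixed cut-off could miss a change made before a late HbA1c sample that is still analysed. Protocol 7.3 continues its prohibitions through follow-up, including new insulin and other DPP-4 inhibitors, and limits an added oral drug to subjects on no other antidiabetic drug. Section 9.3.6 concerns supply after participation is complete; it does not describe switching at Week 52. No document gives a rate of such starts.

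**Against the denominator point.** The effect is small. The SAP does not say how a subject without Period II dosing is coded, and the Handling Rules for Analysis Data, which are not among these documents, might exclude such subjects. Also, by the footnote to the SAP's HbA1c window table, the end-of-Period-II value is counted from the first SYR-472 25 mg tablet. Subjects in the SYR-472 arm who stopped in Period I can thus still contribute one, so in that arm the full analysis set is closer to that analysis. This stands as a qualification. The mismatch remains for the placebo arm and for the Week 16 to 52 visit results, which need a sample on or after Period II Day 2.

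**Against the direction point.** New oral drugs already have their own row, so that form of strengthening is not merged with reductions. One subject can also have both an increase and a reduction, so exclusive categories would not work. In addition, Protocol 9.1.3 specifies Period II recording of name, dose and dates only for newly started oral drugs. These points shape the remedy but do not make the single row informative about direction.

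**On consequence.** The table is descriptive and feeds no model or test, and Period II HbA1c is summarised without a between-group comparison. This stands, and keeps the severity low.

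**Conclusion.** The concern holds in a limited form. Table 1.2.4 under-describes background therapy in Period II: its denominator is not restricted to subjects who could have the event, and it does not show the direction of changes in existing drugs. The dilution is about 1 to 2 percentage points for a true 20% at d of 5% to 10%, and 4 points at d of 20%. These figures assume that subjects not dosed in Period II are coded No and that d applies equally within the tabulated subset. The loss of direction cannot be quantified from the documents, but it is the greater limit on interpretation. Week -16 is an internal inconsistency to reconcile. It would go too far to say that the table gives a wrong figure for long-term efficacy, or that its window is at fault. The primary analysis is unaffected.

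**What to change.** In SAP 1.2.4:

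1. **Denominator.** Use full-analysis-set subjects dosed in Period II and, for the new-drug row, those still on study at Week 16. Add a note that SYR-472-arm subjects who stopped in Period I are outside this denominator but can still contribute an end-of-Period-II HbA1c.
2. **Direction.** Replace the single change row by non-exclusive rows: any increase; any reduction, interruption or stop; none. First confirm that the eCRF captures Period II changes in existing drugs in enough detail. If it does not, state that limitation beside the table.
3. **Selection time point.** Reconcile Week -16 in 1.2.4 and 1.3.2 with the Week -6 row label.
4. **Window.** Keep the 20-day cut-off.

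The cost is SAP wording, reprogramming of one descriptive table, the time-point correction in 1.3.2, one or two extra rows and slightly smaller denominators.

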1.3 Measurement of Compliance Status for Treatment

1.3.1 Study Drug Exposure and Compliance in the Treatment Period

Analysis set:	Safety analysis set	
Analysis variables:	Number of study drug administrations	[1-12, 13-24, 25-36, 37-48, 49-52, 53-Max]
	Number of study drug administrations in Treatment Period I	[1-4, 5-8, 9-12, 13-Max]
	Duration of study drug exposure in Treatment Period I (days)	[1-28, 29-56, 57-84, 85-Max]
	Compliance with study drug for Treatment Period I (%)	[Min≤ - ≤50.0, 50.0< - ≤70.0, 70.0< - ≤90.0, 90.0< - ≤Max]
	Number of administrations of SYR-472 25 mg tablet	[1-12, 13-24, 25-36, 37-48, 49-52, 53-Max]
	Duration of exposure to SYR-472 25 mg tablet (days)	[1-84, 85-168, 169-252, 253-336, 337-364, 365-Max]
	Compliance with SYR-472 25 mg tablet (%)	[Min≤ - ≤50.0, 50.0< - ≤70.0, 70.0< - ≤90.0, 90.0< - ≤Max]
Analysis methodology:	The following analysis will be performed for the above analysis variables by each treatment group and in the consolidated treatment groups.	
	(1) Frequency distributions for categorical variables and summary statistics for continuous variables	

1.3.2 Compliance of Antidiabetic Drugs

Analysis set: Full analysis set

Analysis variables: Compliance with antidiabetic drugs [Fully complied (90% or more), Almost complied (70% or more), Occasionally complied (50% or more), Rarely complied (less than 50%)]

Visits: Weeks -2, 0, 2, 4, 8, 12, 16, 20, 24, 28, 32, 36, 40, 44, 48, 52 or at discontinuation, and 54

Analysis methodology: The following analysis will be performed for the above analysis variables in subjects who are using antidiabetic drugs at Week -16 among the full analysis set by each treatment group and in the consolidated treatment groups.

(1) Frequency distributions at each visit

1.3.3 Compliance of Diet and/or Exercise Therapy

Analysis set: Full analysis set

Analysis variables: Compliance with diet [Fully complied (90% or more), Almost complied (70% or more), Occasionally complied (50% or more), Rarely complied (less than 50%)]

Compliance with exercise therapy [Fully complied (90% or more), Almost complied (70% or more), Occasionally complied (50% or more), Rarely complied (less than 50%)]

Visits: Weeks -2, 0, 2, 4, 8, 12, 16, 20, 24, 28, 32, 36, 40, 44, 48, 52 or at discontinuation, and 54

Analysis methodology: The following analysis will be performed for the above analysis variables by each treatment group and in the consolidated treatment groups.

(1) Frequency distributions at each visit

2 EFFICACY ANALYSIS

The “full analysis set” based on the specifications in the protocol and the “Handling Rules for Analysis Data” will be the main analysis set. For the sensitivity point of view, the “per protocol set” will be used for an analysis performed secondarily on the primary endpoint in order to examine the robustness of the results.

2.1 Primary Endpoints and Analysis Methodology

2.1.1 Primary Analysis

Analysis set: Full analysis set

Analysis variables: Change in HbA1c at the end of Treatment Period I from Week 0

Analysis methodology: The population mean change in HbA1c at the end of Treatment Period I from Week 0 will be compared between the SYR-472 25 mg/SYR-472 25 mg group and placebo/SYR-472 25 mg group based on an analysis of covariance (ANCOVA) model for the change in HbA1c at the end of Treatment Period I from Week 0 with factors of treatment group and HbA1c at Week 0. The same ANCOVA model will be used to calculate the least square (LS) mean and the two-sided 95% confidence interval (CI) for each treatment group, as well as the intergroup difference in the LS mean between the treatment groups (SYR-472 25 mg/SYR-472 25 mg group – placebo/SYR-472 25 mg group) and the two-sided 95% CI.

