7.1 Inclusion Criteria

Subject eligibility is determined according to the following criteria prior to entry into the study:

1. The subject has a diagnosis of type 2 diabetes mellitus.
2. The subject has a fasting C-peptide value of 0.6 ng/mL or higher at the start of the screening period (Week -6) and Week -2 of the screening period.
3. The subject has a hemoglobin value of 10.0 g/dL or higher at the start of the screening period (Week -6) and Week -2 of the screening period.
4. The subject has an HbA1c value of 7.0% or higher but less than 10.0% at Week -2 of the screening period. However, subjects on hemodialysis (patients with end-stage renal failure) with an HbA1c value of less than 7.0% at Week -2 of the screening period are permitted to be enrolled if they have a glycoalbumin value of 20% or higher.
5. <Subjects with a HbA1c value of 7.0% or higher but less than 10.0% at Week -2 of the screening period>

The subject has an HbA1c value difference between the start of the screening period (Week -6) and Week -2 of the screening period within 10.0%* of the HbA1c value at the start of the screening period (Week -6).

<Subjects on hemodialysis (patients with end-stage renal failure) with an HbA1c value of less than 7.0% and glycoalbumin value of 20% or higher at Week -2 of the screening period>

The subject has a glycoalbumin value difference between the start of the screening period (Week -6) and Week -2 of the screening period within 10.0%* of the glycoalbumin value at the start of the screening period (Week -6).

*: rounded to one decimal place

6. The subject has been on a fixed diet and/or exercise therapy (if any) from at least 6 weeks prior to the start of the screening period (Week -6).
7. The subject meets any of the following:
 - The subject has not received any antidiabetic medications (including insulin preparations) from at least 6 weeks prior to the start of the screening period (Week -6).
 - The subject is being treated with 1 oral hypoglycemic drug* starting from at least 6 weeks prior to the start of the screening period (Week -6) at a fixed dose and regimen.

*: Any of the following medications: metformin, acarbose, miglitol, or voglibose

- The subject is being treated with 1 insulin preparation** from at least 6 weeks prior to the start of the screening period (Week -6) at a fixed dose and regimen (≤ 40 units/day).

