3. The criterion was set to require a blood hemoglobin value of 10.0 g/dL or higher in reference to the therapeutic target for renal anemia provided in the “Clinical Practice Guidebook for Diagnosis and Treatment of Chronic Kidney Disease 2012” [7] and “Evidence-based Clinical Practice Guideline for CKD 2013” [8] because a low blood hemoglobin level may affect HbA1c, which is defined as an efficacy endpoint.

4. The criterion was set to define a lower limit of 7.0% because The Evidence-based Practice Guideline for the Treatment for Diabetes in Japan 2013 [9] recommends that the target value of HbA1c should be less than 7.0% from the perspective of prevention of complications. However, since subjects on hemodialysis (patients with end-stage renal failure) may have a low HbA1c level because of factors such as increased immature erythrocytes and shorter erythrocyte lifespan [8], it was decided to take glycoalbumin value additionally into consideration in evaluating subjects with the lower limit of HbA1c level of less than 7.0%. The acceptable glycoalbumin level for such subjects was set at 20% or higher in reference to Best Practice for Diabetic Patients on Hemodialysis 2012 [10]. In addition, the upper limit of HbA1c level was set at 10.0% to exclude subjects with very poor glycemic control with respect to the safety of the subjects.
5. The criterion was set to select subjects with stable glycemic control.
6. The Evidence-based Practice Guideline for the Treatment of Diabetes 2013 [9] recommends to change treatment for patients who cannot achieve the target glucose level despite continuous diet and exercise therapy for 2 to 3 months; therefore, patients who have been on a fixed diet and/or exercise therapy (if any) from at least 6 weeks prior to the start of the screening period (Week -6), i.e., at least 12 weeks prior to the start of Treatment Period I, will be included in this study.

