8.2 Study drug Assignment and Dispensing Procedures

After judging and confirming eligibility of a subject, the investigator or sub-investigator will assign the subject to receive the study drugs for Treatment Period I which have been allocated to each study site (SYR-472DB tablets) in consecutive order of medication ID number. The investigator or investigator's designee will record the medication ID number in the eCRF.

In Treatment Period II, the investigator or sub-investigator will start administration of the study drug for Treatment Period II (SYR-472 25 mg tablet) after performing all physical examinations/examinations/assessments scheduled for Week 12 in the treatment period.

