13.3 Determination of Sample Size

Randomized subjects: 53 subject per group, 106 in total

(Changed as of 12 September 2016)

<Justification of sample size>

In Study CCT-002, the intergroup difference (two-sided 95% CI) in the mean change in HbA1c (JDS value) at the end of the treatment period (value at the end of the treatment period - value at the end of the screening period) between the SYR-472 100 mg group and placebo group was -0.56 ([-0.753, -0.367])%. In the same study, the standard deviation of the change in HbA1c (JDS value) at the end of the treatment period (value at the end of the treatment period - value at the end of the screening period) for each treatment group ranged from 0.523% to 0.628%.

In this study, which will administer SYR-472 at a dose of 25 mg once weekly to patients with type 2 diabetes mellitus complicated by severe renal impairment or end-stage renal failure, the intergroup difference in the mean change in HbA1c at the end of Treatment Period I from the end of the screening period (Week 0) between the SYR-472 25 mg group and placebo group is assumed to be -0.40%, given that the efficacy of SYR-472 25 mg in this study is similar to that of SYR-472 100 mg administered once weekly to patients with type 2 diabetes mellitus not complicated by renal impairment. The common standard deviation in each treatment group is assumed to be 0.80%.

CONFIDENTIAL

Based on these assumptions, 86 subjects per group will be required to provide a 90% power in a two-sample t-test with a significance level of 5% (two-sided). Therefore, the sample size was set at 90 as randomized subjects per group at the start of the study allowing for the possibility that there exit some subjects whose primary endpoint cannot be evaluated.

However, achievement of the sample size as originally planned at the start of the study was found difficult because there were more than expected numbers of candidate subjects who did not provide consent and who dropped out during screening after providing consent for the study. It was therefore decided to change some of the inclusion and exclusion criteria for this study. After these changes, the ultimate number of subjects randomized and evaluable for the primary endpoints are expected to be around 53 and 51, respectively, per group.

Assuming the number of subjects per group as 51 under these assumptions, the study will provide a 70.6% power in a two-sample t-test with a significance level of 5% (two-sided).

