4 SIGNIFICANCE LEVEL AND CONFIDENCE COEFFICIENT

- Significance level: 5% (two-sided tests)
- Confidence coefficient: 95% (two-sided)

History of Revision (version management)

Version	Date	Prepared/modified by	Comments
First Version	16 April 2018	PPD	Preparation of first version
Second Version	12 June 2018		Preparation of second version

[Appendix 1] SYR-472-3003 Comparison Table for Changes

Page	Existing Text	Revised Text	Rationale for Changes
18	
1.2.1 Distribution of Baseline Demographics
 
Rapid-acting insulin secretagogues [Yes]
 
...
 
α-glucosidase inhibitors [Yes]
 
...
 
Insulin preparations [Yes]
 
Mixed [Yes]
 
Intermediate-acting [Yes]
 
Long-acting soluble [Yes]
	
1.2.1 Distribution of Baseline Demographics
 
Rapid-acting insulin secretagogues [Yes, No]
 
Details of rapid-acting insulin secretagogues
 
...
 
α-glucosidase inhibitors [Yes, No]
 
Details of α-glucosidase inhibitors
 
...
 
Insulin preparations [Yes, No]
 
Types of insulin preparations [Mixed, intermediate-acting, Long-acting soluble]
	Adjustment of descriptions and changes in the contents of distributions as a result of reexamination of contents of distributions
19	
1.2.1 Distribution of Baseline Demographics
 
HbA1c (%) (Week 0)
 
[Min\leq - <8.0, 8.0\leq - \leqMax]
	
1.2.1 Distribution of Baseline Demographics
 
HbA1c (%) (Week 0)
 
[Min\leq - <7.0, 7.0\leq - \leqMax]
 
[Min\leq - <8.0, 8.0\leq - \leqMax]
	Addition of distributions as a result of reexamination of contents of distributions
20	
1.2.4 Concomitant Antidiabetic Drugs
 
Permitted in the Study
 
Any change in doses of antidiabetic drugs that are being used at Week -6 and will be concomitantly used during the study period in Treatment Period II
	
1.2.4 Concomitant Antidiabetic Drugs
 
Permitted in the Study
 
Any change in antidiabetic drugs that are being used at Week -6 and will be concomitantly used during the study period in Treatment Period II
	Adjustment of descriptions to clarify the contents of distribution

Page	Existing Text	Revised Text	Rationale for Changes

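### The primary ANCOVA leaves out hemodialysis status, so a chance imbalance in dialysis share can shift the realised estimate modestly; adding the term is a cheap improvement

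*SAP*

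**What the plan says.** **Primary model.** SAP 2.1.1 compares the arms by ANCOVA on the change in HbA1c at the end of Treatment Period I "from Week 0 with factors of treatment group and HbA1c at Week 0". The protocol synopsis and protocol 13.1.3 give the same two terms. SAP 2.1.2(2) repeats the model in the per protocol set.

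**Allocation.** Protocol 8.3 says that randomisation personnel generate a schedule, and names no stratification factor or block rule. Under protocol 8.2 the investigator assigns kits "which have been allocated to each study site (SYR-472DB tablets) in consecutive order of medication ID number". About 50 sites are planned for 106 subjects.

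**Dialysis and HbA1c.** The justification of inclusion criterion 4 (protocol 7.1) says that hemodialysis subjects "may have a low HbA1c level because of factors such as increased immature erythrocytes and shorter erythrocyte lifespan". Those below 7.0% at Week -2 may enter if glycoalbumin is 20% or higher. Criterion 5 then tests their stability on glycoalbumin rather than HbA1c: "The subject has a glycoalbumin value difference between the start of the screening period (Week -6) and Week -2". Dialysis subjects at 7.0% or higher meet the same HbA1c range and stability test as everyone else.

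**Other analyses.** Protocol 13.1.3 also plans an ANCOVA with further baseline characteristics, to be settled at the blind data review and not named. SAP 2.4.1, on covariates, only refers back to 2.1.1. SAP 2.4.8 fits treatment, hemodialysis and their interaction without listing Week 0 HbA1c. SAP 1.2.1 tabulates hemodialysis by arm.

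**The concern.** Hemodialysis is the main division in this population. It is known at baseline for every subject and already coded yes/no in the SAP. By the protocol's own account, the same HbA1c may stand for different glycemia on and off dialysis, and the lowest-HbA1c dialysis subjects are not screened for HbA1c stability. Expected HbA1c change at a given Week 0 value could therefore differ between the two groups.

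If it does, and the arms differ by chance in dialysis share, part of that difference appears in the treatment estimate. No model specified in the SAP contains both hemodialysis and Week 0 HbA1c. An imbalance would show in the baseline table, but no planned analysis would deal with it, and an adjustment chosen after seeing the imbalance would carry little weight. At stake is how well the estimate stands up in the one trial that is run. The validity of the test is not in question.

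**Working it through.** **Inputs from the documents.** "Significance level: 5% (two-sided tests") (SAP 4); a treatment difference that "is assumed to be -0.40"% and an SD stated as "The common standard deviation in each treatment group is assumed to be 0.80"% (protocol 13.3); 53 randomised and 51 evaluable per group, with stated power 70.6% (protocol 13.3).

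**Inputs that must be assumed.** The documents give neither the dialysis share p nor the dialysis effect g, meaning the difference in HbA1c change between dialysis and non-dialysis subjects at equal Week 0 HbA1c. Ranges used: p = 0.2 to 0.5; g = 0.2 to 0.4%.

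**1. The plan's own figures.** Two-sample t-test power by the noncentral t gives 70.56% at 51 per group. The smallest n for 90% is 86 (90.3%; 85 gives 89.99%), which agrees with "86 subjects per group will be required to provide a 90% power in a two-sample t-test". The planned standard error is 0.80 × √(2/51) = 0.158.

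**2. Size of a chance imbalance.** If allocation is unrestricted with respect to dialysis, the SD of the arm difference in dialysis share is √(2p(1−p)/51).

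| p | SD (points) | 1.96 × SD (points) | P(≥10 points) | P(≥20 points) |
|---|---|---|---|---|
| 0.2 | 7.9 | 15.5 | 17% | 0.9% |
| 0.3 | 9.1 | 17.8 | 23% | 2.3% |
| 0.5 | 9.9 | 19.4 | 28% | 3.7% |

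A 20-point imbalance is thus at about the edge of the 95% range when p = 0.5, and beyond it for smaller shares.

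**3. How much passes through.** Shift = k × g × imbalance, where k is the fraction not absorbed by Week 0 HbA1c. Suppose dialysis subjects have Week 0 HbA1c lower by 0.8, with within-group SD 0.7 and p = 0.4 (all assumed). Then k = 0.7² / (0.7² + 0.8² × 0.4 × 0.6) = 0.490 / 0.644 = 0.76. With no baseline gap, k = 1. Simulation (51 per group, 8,000 trials per setting) gave shifts per unit imbalance of 0.17 to 0.18 for g = 0.2 and 0.28 to 0.33 for g = 0.4. With dialysis in the model they were near zero (−0.02 to 0.03, within simulation noise). Across the simulations run for this point, k was about 0.65 to 1.0.

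**4. Shift for a 20-point imbalance.**
- Low end: 0.65 × 0.2 × 0.20 = 0.026, or 0.026/0.158 = 0.16 of a standard error.
- High end: 1.0 × 0.4 × 0.20 = 0.08, or 0.08/0.158 = 0.51 of a standard error.
- A 10-point imbalance gives half of each.

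The sign depends on which arm has more dialysis subjects and on the sign of g.

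**5. Average behaviour of the two-term model.** In the same simulations the mean estimate was about −0.002 under no effect, and −0.397 and −0.396 under a true −0.40. Type I error was 4.8 to 5.0%.

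**6. Power.** Holding total SD at 0.80, adding dialysis leaves a residual SD of √(0.64 − g²p(1−p)). For p = 0.2 to 0.5, power moves from 70.6% to 71.0–71.2% (g = 0.2) or 72.3–73.3% (g = 0.4). The simulations, which used a residual SD of 0.75 and so start higher, gave 75.4% to 76.0% and 73.0% to 74.6%. With g = 0 the largest simulated loss was 0.8 points (70.5% to 69.7%).

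**The case against.** The strongest reply is that chance imbalance is already covered by the confidence interval. The two-term estimate is unbiased over randomisations and its error rate holds. **This stands**, and it limits the point to conditional robustness.

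Second, the protocol supports a difference in HbA1c level on dialysis, not in 12-week change, and a level difference is largely what the baseline covariate handles. The design also limits drift: at least 6 months of hemodialysis in clinically stable subjects, hemoglobin of at least 10.0 g/dL at two screening visits, and background therapy fixed in principle through Treatment Period I. **This stands in part.** No document figure supports any particular g, and 0.4% would equal the whole assumed drug effect. But nothing in the documents shows g to be zero.

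Third, other analyses touch the matter. **They do not close it.** The protocol's covariate-adjusted ANCOVA names no covariates and is not carried into the SAP, and the hemodialysis subgroup model lists no Week 0 HbA1c.

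A reader might also infer stronger things that the documents do not support:
- *That randomisation was unstratified.* The documents are silent; consecutive kits within site suggest it but do not state it.
- *That an imbalance passes in full into the estimate.* Only the part not explained by Week 0 HbA1c does.
- *That the common baseline slope is the fault.* A yes/no dialysis term changes the intercept only, so this remedy would not address a slope difference.
- *That adjustment would repair the 70.6% power.* The gain is too small.

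**Conclusion.** The point holds as a moderate gap in conditional robustness. The primary model omits a baseline factor that the protocol itself links to how HbA1c reads, and no analysis in the SAP adjusts for that factor together with Week 0 HbA1c. Under the assumed effects, a 20-point imbalance moves the estimate by roughly one sixth to one half of its planned standard error, in either direction; most realised imbalances would be smaller.

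This rests on three things the documents do not give: the dialysis share, the residual dialysis effect, and allocation that is unrestricted with respect to dialysis. If randomisation was in fact stratified by dialysis, the imbalance argument largely falls away. The term would still belong in the model, because leaving out a prognostic stratum makes the standard error too large. The sample-size figures reproduce and are unaffected. The reason to act is protection against a conditional shift at almost no cost; power is a side issue.

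**What to change.** Before unblinding, which is the deadline protocol 13.1 sets for the SAP:

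1. In SAP 2.1.1, specify the ANCOVA with treatment group, Week 0 HbA1c and hemodialysis at baseline (yes/no). Carry the same model into the per protocol repeat in SAP 2.1.2(2).
2. Amend the primary analysis in the protocol synopsis and in protocol 13.1.3 to match. Changing the SAP alone would leave the two documents in conflict on the primary model.
3. Keep the two-term model as a named sensitivity analysis.
4. State whether randomisation was stratified, and by what.

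The cost is a protocol amendment, SAP wording and one degree of freedom. No new data are needed. If dialysis turns out not to be prognostic, the loss is under 1 point of power.
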